#### **7.4. Intervention**

The GP will discuss participants' personalised risk estimates for diabetes-related complications and life expectancies associated with different self-management behaviours (~5 minutes). These personalised risk estimates will be calculated by the GP through a validated simulation model (UKPDS-OM [32]). According to personal characteristics (age, gender, ethnicity...) and risk factors (duration of diabetes, history of complications, blood glucose level...), the UKPDS-OM allows to compute, for each individual, their own (personalised) risk estimates of developing diabetes-related complications and life expectancies.

#### **7.5. Intervention Effects**

In the unlikely event of a negative effect of the intervention on risk perceptions and/or self-management behaviour found after data analysis, the CI will inform the GP. Personal details of participants will be kept separate from research data, and the CI will use ID numbers to refer to a given participant. The use of ID numbers will be limited for the purpose of giving feedback to the GP after data analysis.

In case a positive effect on risk perceptions and self-management behaviour is found in the intervention group, the intervention will also be offered to participants in the control group at their next consultation visit.

#### **7.6. Discontinuation/Withdrawal of Participants from Study**

Each participant has the right to withdraw from the study at any time. In addition, the Investigator may discontinue a participant from the study at any time if the Investigator considers it necessary for any reason including withdrawal of consent. Data collected up to the withdrawal will be used.

#### **7.7. Definition of End of Study**

The end of study is the date when the questionnaire of the last participant will have been filled out.

### **8. STATISTICS AND ANALYSIS**

#### **8.1. Description of Statistical Methods**

Frequencies and percentages will be used to describe categorical variables, and means  $\pm$  SD to describe continuous variables.

Pre-post intervention differences between groups in terms of study outcome variables will be tested using Chi-square and Student t-tests, whereas pre-post intervention differences within groups will be tested using McNemar and paired t-tests.

The Kappa test will be used for detecting the degree of agreement between pre- and post-perceived risk with baseline objective risk.

In the intervention group, correlation between appropriateness of risk perceptions and self-management scores (post-intervention) will be tested by means of point biserial correlation. Finally, Pearson and Spearman correlations will be used to test for correlations between observable characteristics and outcome variables.

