Recent studies have shown that people with T2DM largely underestimate their risks of developing complications. [15] Existing risk communication interventions have shown mixed results, with many participants barely understanding the explanations of health professionals about risks and having poor recall of risk information [16-18]. In this context, there is a need for better risk communication interventions. [15] Rather than increasing the quantity of information to be communicated ('less is often more' [19]), it is necessary to improve its quality. New interventions that make use of patients' decision-making biases are considered to be very promising in the risk communication field [20-22]. We believe that such interventions, through which personalised risks are communicated, will help to correct erroneous risk perceptions, and, in turn, have a greater impact on self-care behaviours.

Based on the results of recent studies investigating the risk perceptions and risk attitudes of people with T2DM, we have developed a new, tailored risk communication intervention. This intervention aims to increase patients' awareness of their risks for complications associated with T2DM and, in turn, to encourage the adoption of recommended self-care behaviours. The objectives of the full trial are to assess the feasibility and measure the expected impact of such an intervention, in order to inform the design of a larger study (RCT to be conducted in the future).

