#### 4. OBJECTIVES AND OUTCOME MEASURES

Objectives	Outcome Measures	Timepoint(s) of evaluation of this outcome measure (if applicable)
To assess the feasibility of a larger study.	Feasibility of study protocol, consent rate, acceptability of	After the study.

	intervention, retention rate, rates of missing data.	
To assess the effectiveness of the intervention in patient's awareness of risks for complications associated with Type 2 diabetes.	Change in risk perception scores.	
 
• Baseline (right before the intervention).
 
• Baseline (right after the intervention).
 
• After 12 weeks.
 

To assess whether the intervention encourages the adoption of recommended self-care behaviours.	Change in self-management behaviour scores.	
 
• Baseline (right before the intervention).
 
• After 12 weeks.
 

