### **7.3. Procedure**

- Visit 1

For participants who gave their informed consent, the CI will administer the study questionnaires that measures risk perceptions and assesses self-management behaviour (~10 minutes). [23, 33]

After the first set of questionnaires are completed, all participants will attend their routine clinical consultation with their GP. During the consultation, half of the participants will receive the risk communication intervention from the GP (intervention group, ~5 minutes) and half of the participants will not (control group). Participants will be randomised into the intervention or the control group by means of a list drawn up by a computerised randomisation program. They will be attributed with an order number and this number will be randomly allocated into one of the two groups. The participant will be blind to their allocation but the CI will not be.

Right after the consultation, risk perceptions of all participants (i.e. in both groups) will be measured by the CI once again (~5 minutes), to account for potential effect of the consultation on the control group.

- Visit 2

At participants' next consultation visit, which will be approximately 12 weeks after the intervention, the same questions about risk perceptions and self-management behaviour will be asked by the CI right before the consultation (~10 minutes).

The interest of face-to-face appointments is that it ensures reliability in participants' answers, as compared to email or telephone interviews.

This methodology has been used in most recent studies that aimed at measuring the impact of risk communication interventions. [17, 24, 25]

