## 8.2. The Number of Participants

40 participants will be recruited (20 in the intervention group, 20 in the control group).

According to Connelly (2008), extant literature suggests that a pilot study sample should be 10% of the sample projected for the larger parent study. [26] Isaac and Michael (1995) suggested 10 - 30 participants [27]; Hill (1998) suggested 10 to 30 participants for pilots in survey research [28]; Julious (2005) in the medical field [29] and van Belle (2002) suggested 12 [30]; Treece and Treece (1982) suggested 10% of the project sample size. [31]

Existing studies of reference used the following sample sizes:

Welschen et al (2012) [17]: 261

Asimakopoulou et al (2008) [24]: 95

Tawfik & Mohamed (2016) [25]: 180

Based on these observations, we decided to take the size of the bigger sample as reference (n=261) and to apply the 10% rule. However, in order to allow for drop-outs and facilitate comparison between the two arms, we decided to add a margin and target 40 participants in total.

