## 8.3. Analysis of Outcome Measures

We will analyse the following outcome variables:

- Feasibility of a larger study: in order to inform the design of a larger study, we will assess the following criteria: integrity of study protocol, consent rate, acceptability of intervention, expected impact of intervention.
- Appropriateness of risk perceptions: we will compare participants' perceived risks to their personalised risk estimates computed via a validated simulation model (UKPDS-OM [32]).
- Self-management scores: we will assess participants' adherence to self-care activities using two validated questionnaires: 1) The Summary of Diabetes Self-Care Activities Measure (SDSCA) [23]; 2) The 8-Item Morisky Medication Adherence Scale (MMAS-8) [33]

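### The between-group t-test on pre-post differences ignores baseline; for the continuous scores ANCOVA is usually more precise and costs at most about 3% in variance at 20 per arm

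*Combined protocol and SAP*

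**What the plan says.** Section 8.1 gives the between-group analysis in one clause: "Pre-post intervention differences between groups in terms of study outcome variables will be tested using Chi-square and Student t-tests". Within-group differences go to McNemar and paired t-tests. Regression, ANCOVA and baseline adjustment appear nowhere in the document.

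Section 4 defines one secondary outcome as "Change in self-management behaviour scores", measured before the intervention and after 12 weeks. Section 8.3 says the trial will assess "adherence to self-care activities using two validated questionnaires", namely the SDSCA and the MMAS-8. Section 7.3 has everyone complete the questionnaires before the first consultation, and at visit 2 "the same questions about risk perceptions and self-management behaviour will be asked by the CI right before the consultation". The baseline value is therefore already collected in both arms.

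On scale, section 8.1 adds that "correlation between appropriateness of risk perceptions and self-management scores (post-intervention) will be tested by means of point biserial correlation". A point biserial correlation pairs a binary variable with a continuous one. Here appropriateness of risk perception is the binary variable and the self-management score the continuous one.

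On purpose, section 3 says the aim is to "measure the expected impact of such an intervention, in order to inform the design of a larger study", and section 8.3 lists the feasibility criteria as "integrity of study protocol, consent rate, acceptability of intervention, expected impact of intervention".

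**The concern.** A t-test on change scores subtracts the whole baseline value from each participant's follow-up value. That is the most efficient use of the baseline only when the regression slope of follow-up on baseline (correlation × post SD / pre SD) is near 1. When the slope is lower, as it is with moderate correlation and similar SDs, subtracting the full baseline adds noise. ANCOVA estimates the slope from the data instead.

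The wording could also mean comparing the arms at each time point. That reading makes no use of the baseline at all, so the concern stands under either.

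What is at stake is the precision of the impact estimate that the larger study is to draw on. With 20 per arm it will be imprecise whatever the method, and the planned test usually makes it less precise than the same data allow. The point is firm for the SDSCA and MMAS-8 scores at 12 weeks. For risk perception, just after the consultation and at 12 weeks, it applies only if a continuous score is analysed. Sections 1 and 4 speak of scores, but the kappa and point biserial methods suggest a categorical variable.

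**Working it through.** **Inputs**

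- From section 8.2: "40 participants will be recruited (20 in the intervention group, 20 in the control group"), so n = 20 per arm.
- From section 8.1: unadjusted t-test.
- Not in the documents, so assumed and ranged: correlation ρ between baseline and follow-up (0.3, 0.5, 0.7, 0.9) and ratio k of post SD to pre SD (0.8 to 1.25). Pre SD is set to 1.
- The plan states no power, alpha or precision for this comparison, so it has no figure of its own to reproduce.

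**Formulas** (variance of the group difference = factor × 2/n)

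- Change score: 1 + k² − 2ρk
- ANCOVA: k²(1 − ρ²) × [1 + 1/(2n − 4)]; the bracket is the average price of estimating the slope, 37/36 = 1.028 at n = 20
- Follow-up only: k²

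Before that price, the change-score factor exceeds the ANCOVA factor by (1 + k² − 2ρk) − k²(1 − ρ²) = (1 − ρk)², which is never negative. The variance ratio ANCOVA/change therefore cannot exceed 37/36.

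**Example**, k = 1, ρ = 0.5: change = 1 + 1 − 1 = 1.000; ANCOVA = 0.75 × 37/36 = 0.771; ratio 0.771.

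**Variance ratio ANCOVA/change, n = 20**

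| k | ρ = 0.3 | ρ = 0.5 | ρ = 0.7 | ρ = 0.9 | ANCOVA less precise when |
|---|---|---|---|---|---|
| 0.8 | 0.516 | 0.587 | 0.645 | 0.625 | never |
| 0.9 | 0.597 | 0.686 | 0.772 | 0.832 | never |
| 1.0 | 0.668 | 0.771 | 0.874 | 0.976 | ρ above 0.946 |
| 1.1 | 0.730 | 0.840 | 0.947 | 1.027 | ρ 0.812 to 0.957 |
| 1.25 | 0.806 | 0.918 | 1.008 | 0.976 | ρ 0.677 to 0.879 |

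**95% CI half-width**, k = 1, in SD units: t(0.975, df) × √(factor × 2/20), with df 38 for change and 37 for ANCOVA.

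| ρ | Change | ANCOVA |
|---|---|---|
| 0.3 | 0.757 | 0.620 |
| 0.5 | 0.640 | 0.563 |
| 0.7 | 0.496 | 0.464 |
| 0.9 | 0.286 | 0.283 |

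**Worst case for ANCOVA.** Variance is 2.8% larger. The half-width ratio is t(0.975, 37)/t(0.975, 38) × √(37/36) = 1.0147, or 1.5% wider. If drop-out left 16 per arm (assumed), the slope price is 29/28: 3.6% in variance and 1.9% in half-width.

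**If follow-up values alone are compared.** ANCOVA/follow-up = (1 − ρ²) × 37/36 = 0.935, 0.771, 0.524 and 0.195. Break-even is ρ = √(1 − 36/37) = 0.164.

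**Simulation.** With 40,000 trials per cell and n = 20, the ratios at k = 1 were 0.672, 0.765, 0.879 and 0.979, and both estimators averaged the true effect. With skewed, bounded 0–8 integer scores (30,000 trials per cell), the ratios were 0.656, 0.749, 0.846 and 0.960 at underlying correlations of 0.3, 0.5, 0.7 and 0.9, and the average slope price was again 2.8%.

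**The case against.** The strongest reply is that this is a preference about efficiency. The change-score test is valid and unbiased under randomisation, it matches the outcome as defined, and it concerns secondary outcomes of a feasibility pilot with no precision target to miss. All of that is true and limits the weight of the point. It does not remove it, because sections 3 and 8.3 make expected impact something the pilot is to deliver.

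Second, the 3% bound is an average over randomisations with 20 analysed per arm, and 20 is the number recruited. This stands as a qualification. The bound is 3.6% at 16 per arm and 4.5% (1/22) at 13. In a single trial with 20 per arm the penalty is t²/38, where t is the baseline-imbalance statistic: median 1.2%, 95th percentile about 10.8%. But the planned test also suffers under such imbalance. The baseline difference has a standard error of √(2/20) = 0.32 SD, and an imbalance of that size at slope 0.5 shifts the change-score estimate by about (1 − 0.5) × 0.32 = 0.16 SD. ANCOVA adjusts for it.

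Third, the gain rests on assumed correlations and SD ratios. That is correct: across the grid it runs from a 48% reduction in variance to a loss of under 3%. The size of the gain in this trial is unknown; the cap on the average loss does not depend on those inputs.

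Fourth, section 8.1 does not map each test to an outcome, and no scoring rule is given for either questionnaire. This is fair, and it is why risk perception is included only conditionally. For self-management, the point biserial correlation makes a continuous score the clear reading.

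Finally, the CI in the proposed wording does not follow from the efficiency argument. It is there because section 8.1 names only tests, whereas planning a larger study needs an estimate and its uncertainty.

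**Conclusion.** The concern holds as a loss of efficiency; no stated figure is wrong and the planned test is not invalid. With equal SDs and 20 per arm, the change-score t-test has about 50%, 30%, 14% and 2% more variance than ANCOVA at correlations of 0.3, 0.5, 0.7 and 0.9 (1/0.668, 1/0.771, 1/0.874 and 1/0.976). It is better only when the slope is close to 1, and then by at most 2.8% on average. If follow-up values alone are compared, ANCOVA is better at any correlation above about 0.16. These sizes depend on assumed correlations and SD ratios. The conclusion is firm for the self-management scores and conditional for risk perception. The consent, retention and missing-data outcomes and the categorical comparisons are not touched.

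**What to change.** Add to section 8.1: *For each continuous score (each SDSCA and MMAS-8 score at 12 weeks; risk perception after the first consultation and at 12 weeks, where it is scored continuously), the between-group difference will be estimated by linear regression of the follow-up value on randomised group and the baseline value (ANCOVA), and reported with its 95% CI.*

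State whether risk perception is analysed as a score or as a binary appropriateness variable, and keep the planned categorical methods if it is binary. The outcome can still be described as change, because regressing the change score on group and baseline gives the same group coefficient.

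The cost is one sentence and one residual degree of freedom (38 to 37 with 20 analysed per arm). No new data or visits are needed. If the true slope is near 1, up to about 3% in variance is lost on average, slightly more with drop-out.

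### Section 8.1 plans within-arm significance tests beside the between-group tests without saying which supports a statement of effect, so change shared by both arms could be credited to the intervention

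*Combined protocol and SAP*

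**What the plan says.** Section 8.1 first plans the comparison that randomisation supports: "Pre-post intervention differences between groups in terms of study outcome variables will be tested using Chi-square and Student t-tests". The sentence continues: "whereas pre-post intervention differences within groups will be tested using McNemar and paired t-tests". The within-arm analyses are therefore formal tests. They come on top of the descriptive summaries that open the section ("Frequencies and percentages will be used to describe categorical variables", with means and SDs for continuous variables). Section 8.1 gives neither set of tests precedence.

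Other sections show between-arm intent. Section 8.2 enlarges the sample partly to "facilitate comparison between the two arms". In section 7.3, "all participants will attend their routine clinical consultation with their GP", and risk perceptions are measured again in both arms straight afterwards, "to account for potential effect of the consultation on the control group".

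Section 7.5 attaches actions to the findings. One concerns a "negative effect of the intervention on risk perceptions and/or self-management behaviour found after data analysis", which is reported to the GP. The other begins "In case a positive effect on risk perceptions and self-management behaviour is found in the intervention group" and leads to the intervention being offered to controls. Section 8.3 lists the expected impact of the intervention among the criteria that inform a larger study.

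Section 8.1 also plans a point biserial correlation between appropriateness of risk perceptions and self-management scores, in the intervention arm only and on post-intervention values.

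**The concern.** A paired t-test or McNemar test within one arm asks whether that arm changed. It cannot say whether the intervention caused the change, because the consultation, answering the same questions again, and regression to the mean can each move both arms. The protocol itself names the first of these for risk perceptions. If the consultation shifts answers, the two kinds of test planned in one sentence can disagree, and the plan does not say which one counts.

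What is at stake is the secondary effectiveness objective and the expected-impact figure passed to a larger study. The wording of section 7.5 adds to the risk, since an effect found in the intervention group could mean a one-arm result or the between-group comparison of section 8.1.

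**Working it through.** **Inputs from the documents.** 20 participants per arm (sections 6.1 and 8.2), randomised (section 7.3). Section 4 measures risk perceptions before the intervention, right after it and at 12 weeks, and self-management at baseline and 12 weeks. The plan gives no figure for this point to reproduce.

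**Assumptions.** The documents give no significance level, SD, size of shared change or drop-out rate. I take two-sided 0.05, count only the favourable direction, set the intervention effect to zero, and give both arms the same mean change d, in units of the SD of change. This is applied to risk perceptions only, because the documents foresee no shared change in self-management.

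**Paired t-test, intervention arm.** The statistic follows a noncentral t with n − 1 df and noncentrality d√n, and is significant above t(0.975, 19) = 2.093. For d = 0.3, 0.5, 0.7 and n = 20 the noncentrality is 1.34, 2.24, 3.13.

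| | d = 0 | d = 0.3 | d = 0.5 | d = 0.7 |
|---|---|---|---|---|
| Intervention-arm paired t significant | 2.5% | 24.6% | 56.4% | 84.4% |
| Between-group t on change significant (simulated for d > 0) | 2.5% | about 2.5% | about 2.5% | about 2.5% |
| Intervention-arm test significant, between-group test not (simulated) | – | 22.4% | 53.8% | 81.9% |
| Intervention arm significant, control arm not: p(1 − p) | – | 18.6% | 24.6% | 13.2% |

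For the last row at d = 0.5: 0.564 × 0.436 = 0.246. With an assumed 20% drop-out (16 per arm) the first row becomes 20.2%, 46.5% and 74.5% for d = 0.3, 0.5 and 0.7.

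**McNemar.** Suppose both arms move from an assumed 30% appropriate to 50%, 60% or 70%, with 5% moving the other way. The gain probabilities are then 0.25, 0.35 and 0.45 (for example 0.30 + 0.25 − 0.05 = 0.50). Full enumeration with n = 20 gives an exact McNemar test significant in 19.6%, 45.5% and 69.4% of trials. A between-arm Chi-square on the post-consultation proportions gives 2.1%, 2.4% and 2.7%.

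**Precision of the between-arm estimate.** The 95% CI half-width for the difference in mean change is t(0.975, 2n − 2) × √(2/n). With n = 20 this is 2.024 × 0.316 = 0.64 SD of change; with n = 16 it is 2.042 × 0.354 = 0.72. Both are before baseline adjustment.

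**Correlation.** The critical value is t/√(df + t²). With n = 20 (18 df) it is 0.44. For a partial correlation in all 40 participants, adjusted for arm and baseline (36 df), it is 0.32. One is a simple and the other a partial correlation, so the difference is not a like-for-like gain in precision.

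**The case against.** The strongest reply is that the correct analysis is already planned and named first, and the within-arm tests follow as a separate question. A reader might infer that the trial will judge effectiveness within arms. No section says so. A reader might likewise take section 7.5 as a one-arm decision rule. Its wording allows that, but its other paragraph speaks of an effect of the intervention, which fits the between-group comparison equally well. Both points stand.

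The re-measurement in section 7.3 is also a safeguard: the investigators foresaw the consultation effect and collect control data to deal with it. Looking at change in the control arm is a sensible use of those data, and the fix keeps it as a description.

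The percentages above are, strictly, the power to detect a real change in one arm. They become error rates only if that change is credited to the intervention, and they depend on a shift the documents do not give. This too stands.

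Two neighbouring issues should not add weight. Section 8.1 does not say which post-intervention risk-perception measurement is tested, but that is missing detail. The one-arm correlation is not presented as an effect estimate, and association among those who received the intervention is a legitimate question.

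What survives is narrower: formal tests that cannot isolate the intervention stand beside the test that can, with no stated order, in a design that expects the consultation may have its own effect.

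**Conclusion.** The point holds as an inexpensive improvement that should be made, not as a planned error. With 20 per arm, no intervention effect and an assumed shared shift of 0.3 to 0.7 SD of change, the intervention-arm test would be significant in roughly a quarter to five-sixths of trials, while the between-group test stays at about 2.5%. Without a shared shift the inflation disappears. The consequence is limited because feasibility is the primary objective, effectiveness is secondary, and harm requires a within-arm result to be read as an effect. The documents do not support a claim that the between-group analysis is missing, or that self-management is expected to drift in both arms.

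**What to change.** In section 8.1, state that conclusions about the intervention, including expected impact under section 8.3, rest on the between-arm difference with its 95% CI, adjusted for the baseline value of the same outcome:

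- Scores: regression of the follow-up score on arm and baseline score.
- Categorical outcomes: a difference in proportions adjusted for baseline status where numbers allow; otherwise unadjusted, with baseline proportions shown alongside.
- Timepoints: risk perceptions right after the consultation and at 12 weeks; self-management at 12 weeks.

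Report within-arm change descriptively (mean with SD or CI, or n and %), including the control arm's change with the consultation, and state that it is not evidence of an intervention effect. Reconcile the wording of section 7.5 with the between-arm comparison in section 8.1; what is then offered stays with the sponsor and the GP.

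Optional and exploratory: keep the planned intervention-arm correlation, and add the association in all randomised participants with data, adjusted for arm and baseline self-management score and also shown by arm. This answers a somewhat different question and assumes a common association across arms.

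The cost is wording and analysis code, with no new data or visits. The within-arm p-values are lost, and the between-arm intervals will be wide (the ±0.64 SD above). Where a categorical outcome cannot be adjusted, chance baseline imbalance stays in the estimate.

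### Section 8.1 compares the arms on continuous outcomes without adjusting for the baseline value collected in both arms; adjusting would usually give a narrower interval at almost no cost.

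*Combined protocol and SAP*

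**What the plan says.** **Arm comparison.** Section 8.1: "Pre-post intervention differences between groups in terms of study outcome variables will be tested using Chi-square and Student t-tests". Within-arm changes are to be tested with McNemar and paired t-tests. No baseline-adjusted model appears anywhere in section 8.

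**Data available.** Under section 7.3, risk perceptions and self-management are recorded at visit 1 before the consultation, for all consenting participants. After the consultation, "risk perceptions of all participants (i.e. in both groups) will be measured by the CI once again". At visit 2, "the same questions about risk perceptions and self-management behaviour will be asked by the CI right before the consultation". The table in section 4 agrees: risk perception has two follow-ups ("Baseline (right after the intervention" and "After 12 weeks"), while self-management has only the 12-week one.

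**Use of the result.** Feasibility is the primary objective (sections 1 and 4). Section 8.3 counts the likely impact of the intervention among the criteria that inform the larger study.

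**Perception-behaviour association.** Section 8.1: "In the intervention group, correlation between appropriateness of risk perceptions and self-management scores (post-intervention) will be tested by means of point biserial correlation". No reason is given for leaving out the controls. The later Pearson and Spearman correlations concern observable characteristics, so they do not cover this association in controls.

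**The concern.** The arms are randomised, and the baseline is taken before the consultation at which their care diverges. Adjusting for it is therefore legitimate, and the data are already in hand. A change score subtracts the whole baseline value, which is too much unless the pre-post correlation is close to 1. A comparison of follow-up values alone ignores the baseline altogether. A regression on baseline estimates the right amount to remove.

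With 20 per arm every interval will be wide, so avoidable imprecision matters. What is at stake is how tightly the pilot can state an arm difference for use in planning the later RCT. The validity of the trial is not at stake.

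**Working it through.** **The plan's own figure.** Section 8.2 takes 10% of 261: 0.10 × 261 = 26.1. It then adds an unquantified margin to reach 40. The documents give no power, SD, pre-post correlation or interval width, so there is no precision figure to reproduce.

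**Inputs.** 20 per arm (sections 6.1 and 8.2). Assumed: equal SD of 1 at baseline and follow-up, two-sided 95% intervals, and a pre-post correlation ρ of 0.3 to 0.9.

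**Formulas for the half-width, in SD units.**
- t-test on change: t(38) × √[2 × 2(1 − ρ)/20]
- t-test on follow-up values: t(38) × √(2/20)
- Follow-up adjusted for baseline: t(37) × √[2(1 − ρ²)/20] × √(1 + 1/36). The last factor is the small-sample cost of estimating the baseline slope.

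Here t(38) = 2.024 and t(37) = 2.026. At ρ = 0.5:
- Change: 2.024 × √0.100 = 0.640
- Adjusted: 2.026 × √0.075 × 1.014 = 0.563
- Ratio: 0.563/0.640 = 0.88

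| ρ (assumed) | Change | Follow-up only | Adjusted | Narrower than change | Narrower than follow-up only |
|---|---|---|---|---|---|
| 0.3 | 0.757 | 0.640 | 0.620 | 18% | 3% |
| 0.5 | 0.640 | 0.640 | 0.563 | 12% | 12% |
| 0.7 | 0.496 | 0.640 | 0.464 | 6% | 28% |
| 0.9 | 0.286 | 0.640 | 0.283 | 1% | 56% |

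At ρ = 0.95 the advantage over the change score has gone (0.203 against 0.202).

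**With losses.** With 16 per arm (an assumed 20% loss), change against adjusted is 0.854 to 0.702, 0.722 to 0.637 and 0.559 to 0.526 at ρ = 0.3, 0.5 and 0.7. The percentages are the same.

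**Simulation check (8,000 runs).** Type I error is about 5% for both methods. Power for an assumed 0.6 SD effect is 0.35 against 0.49, 0.46 against 0.56, and 0.67 against 0.73 at ρ = 0.3, 0.5 and 0.7.

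**The correlation.** Fisher z intervals at an assumed r = 0.3:
- Intervention arm only, SE = 1/√17: −0.16 to 0.66
- All 40, adjusted for arm, SE = 1/√36: −0.02 to 0.56

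The second interval is narrower, but it surrounds an average of the two arms. With equal weights, an intervention slope of 0.3 and a control slope of 0 give 0.5 × 0.3 + 0.5 × 0 = 0.15; a control slope of 0.5 gives 0.40. If appropriateness is a yes/no flag, an arm's weight is n_yes × n_no/20. Assume 80% appropriate in the intervention arm and 40% in controls. The weights are then 16 × 4/20 = 3.2 and 8 × 12/20 = 4.8, so controls carry 4.8/8.0 = 60%.

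A check of equal slopes has a 95% margin of 1.96 × √(2/17) = 0.67 on the Fisher z scale. A true difference between r = 0.3 and r = 0 is only 0.31 on that scale, so 20 per arm cannot settle it. In simulation with a slope of 0.8 in the intervention arm and 0 in controls, power was 0.22 pooled against 0.39 for the intervention arm alone.

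**The case against.** **The primary objective is feasibility.** This stands. A half-width of 0.56 SD instead of 0.64 SD is still too wide to fix an RCT effect size, and section 8.3 sets no threshold that would change. The point is therefore a cheap improvement to a secondary estimate.

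**The sentence on arm comparisons is ambiguous.** It may mean t-tests on change, which the outcome wording in sections 1 and 4 favours, or t-tests on follow-up values. The ambiguity alters the size of the gain but not its direction at correlations of 0.3 to 0.9. Against follow-up values alone, the gain is about 3%, 12% or 28% at 0.3, 0.5 or 0.7.

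**The gain depends on an unknown correlation.** This stands. If the change-score reading is right and the correlation is 0.9 or more, there is almost nothing to gain, though also almost nothing to lose.

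**Stronger readings that a reader might infer.**
- *The t-tests are invalid.* They are not: under randomisation they hold their error rate and are merely less efficient.
- *The intervention-only correlation wastes half the data.* The documents do not support this. The planned analysis concerns patients who received the intervention, and a pooled slope is another quantity. The correlation serves no objective in sections 1 or 4 and no decision rule.
- *Appropriateness cannot be computed for controls, because section 7.4 says "These personalised risk estimates will be calculated by the GP through a validated simulation model" only when describing the intervention.* Section 8.3 refers to participants without limiting the arm, and the kappa analysis of "the degree of agreement between pre- and post-perceived risk with baseline objective risk" is not limited either. The calculation for controls is implied.

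The cut-off for appropriateness and the perception timepoint used in the correlation are indeed unstated. These are missing details, not evidence of a wrong analysis.

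**Conclusion.** The point holds as an efficiency improvement worth considering. Section 8.1 makes no use of baseline as a covariate in its between-arm tests of continuous outcomes, although the baseline is planned for everyone. On the change-score reading, adjustment narrows the 95% CI by 18%, 12% or 6% at an assumed pre-post correlation of 0.3, 0.5 or 0.7, and by about 1% at 0.9. These figures assume equal SDs at the two times and 20 per arm; the correlation itself is not in the documents.

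The result bears on the secondary estimate of impact and leaves the feasibility objective untouched. It covers outcomes analysed as continuous scores; categorical appropriateness is outside these figures.

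The restriction of the correlation to the intervention arm is not a defect. An all-participant estimate may sit beside it as exploratory, on the condition that similar slopes are assumed and cannot be verified here.

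**What to change.** In section 8.1, replace the between-arm t-test for each continuous outcome with a linear model of the follow-up value on arm and the baseline value of the same measure. Report the adjusted arm difference with its 95% CI. Apply it at every planned follow-up: risk perception right after the consultation and at 12 weeks, and SDSCA and MMAS-8 separately at 12 weeks. Naming the 12-week value alone would drop the immediate between-arm comparison of risk perception, so both times should be listed.

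Optional and labelled exploratory: keep the planned intervention-only correlation. Add the same association in controls and an arm-adjusted estimate in all participants, showing both arm-specific slopes. Do not report a pooled correlation without adjustment for arm. The same edit could usefully state the cut-off, the perception timepoint, and that baseline UKPDS-OM risk is computed for controls.

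The cost is a few sentences and one degree of freedom. No visits, questionnaires or participants are added.
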